5.2. Study Days

Following the 7-day pre-study period, which includes time for analysis of the blood and urine, eligible IPF patients will return to the clinic and be admitted to the 21-day study. On the first day of the study, these patients will have a physical exam and their vital signs will be recorded. Then, their degree of nasal inflammation and erythema will be evaluated and recorded as before, as will their SaO2, FEV1 and FVC levels and frequency of coughing. Patients will be instructed on how to self-administer their first dose of the nasal spray drug (0.2% sodium pyruvate in 0.9% sodium chloride solution) by first forcefully expelling air from their lungs, and

then spraying 3 squirts of the drug into each nostril, and then forcefully inhaling the drug so that the drug is inhaled into the lungs. After 1 hour, the subjects will have their vital signs taken again. Efficacy and safety evaluations will occur at this 1-hour time period, too, and then again at 2 and 3 hours. The subjects will fill out the product evaluation questionnaire, be given a daily data log form and be given enough drug to last for 21 days (3 bottles), and released from the clinic.

For the next 21 days, subjects will self-administer 3 squirts per nostril of the nasal spray, as instructed, 3 times daily; upon wakening, noon/midday, and before bedtime, Additionally, they will fill out the Daily Data Log form each day to record the number of daily coughs. Patients will be contacted by phone every 2 days to review symptoms and protocol compliance.

On days 8, 14 and 22, they will return to the clinic and have their blood analyzed, vital signs taken, and their degree of nasal inflammation, erythema and cellular morphology recorded. As before, they will be tested for FEV_1 , FVC and SaO_2 levels. The number of coughs they experienced and other information will be discussed with the clinician. They will fill out the product evaluation questionnaire and the CRDQ, and they will then be released from the study on day 22. These data will then be evaluated.

6. Criteria for Patient Selection, Exclusion of Patients, and Number of Patients 6.1. Subject Selection and Number of Patients to be Studied

The patient population is adult patients \geq 40 years old with mild to moderate IPF with FVC and FEV1 values \geq 50% of predicted values. IPF is defined in accordance with the most recent collaborative guidelines from the American Thoracic Society, the European Respiratory Society, the Japanese Respiratory Society, and the Latin American Thoracic Association (56) including HRCT scan and/or lung biopsy consistent with unusual interstitial pneumonia (UIP), especially honeycombing, without identifiable cause related to other ILD such as drug toxicity, occupational or environmental exposure or connective tissue disease.

The study goal will be to enroll 25 patients with confirmed IPF into the trial in the sodium pyruvate (N115) treatment group and 25 with confirmed IPF to be enrolled in the trial in the placebo group. Efforts will be made to include women and minorities. The study will be a randomized, double-blinded placebo-controlled trial to subjects and study investigators.

6.2. Inclusion Criteria

- Individuals with a clinical diagnosis of idiopathic pulmonary fibrosis as determined by clinical evaluation and lung function tests (56), with a condition-related cough.
- Mild to moderate FEV₁ and FVC at 50% or greater of standard
- Individuals who agree to abstain from sexual intercourse, or agree to use condoms or vaginal diaphragms or other devices designed to prevent contraception, during the entire course of the study.

6.3. Exclusion Criteria

- Pulmonary disease other than idiopathic pulmonary fibrosis.
- Respiratory infections in the last 2 weeks.

- Clinically significant cardiac disease including uncontrolled congestive heart failure and unstable angina.
- Pregnancy (urine pregnancy test will be performed prior to enrollment).
- Females of childbearing potential age not on adequate contraception or lactating females.
- Subjects less than 18 years of age.
- Hospitalization within last 6 months due to acute exacerbation of airway disease.
- Subjects with a clinically significant abnormal chest X-ray within past 12 months.
- Medication changes within 1 month of study entry except for antiviral, antibiotic, or antimicrobial medications as well as corticosteroids, antihistamines, or anti-inflammatory medications.
- Subjects who have participated in another drug treatment study within the last month.
- Subjects with a current history of alcohol or recreational drug abuse.
- Subjects who have taken dietary supplements containing pyruvate within 24 hours prior to the screening visit.
- Subjects with metabolic diseases (diabetes, hypoglycemia, etc.).

6.4. Inclusion of Women and Minorities

Every attempt will be made to include all genders and minorities that present with pulmonary fibrosis and are not exempted due to exclusion criteria.

7. Study Design

Assignment of Subject Number and Randomization

This is a randomized placebo-controlled double-blinded trial. Upon enrollment, each subject will be sequentially issued a unique subject number starting at 100. Once a number has been assigned to a subject, it cannot be re-assigned to another subject. Subjects will be encouraged to complete the study, although they may withdraw at any time without prejudice. Termination will be reported to the sponsor in a timely manner. Details of the reason(s) why a subject was dropped or withdrew from the study will be documented. Enrollment will continue until the number of subjects specified in the protocol has been attained. The data from all subjects that have been given a study compound will be retained for analysis.

8. Randomization

The subjects will be randomized to the placebo control or N115 drug study groups using a random number set.

9. Telephone Communication

Subjects will be instructed to call the clinic should they be experiencing any self-perceived adverse events, or if they have any study-related questions. All telephone information will be documented.

10. Products Description (How Administered)

The product is an all-natural patented 0.2% sodium pyruvate in 0.9% sodium chloride nasal spray solution, pH 7.2, with 0.02% benzalkonium chloride as a preservative. The patient will be instructed on the use of the nasal spray prior to the start of the clinical trial. The plastic bottle contains 30 mL. It is non-steroidal. Patients will forcibly expel air from their lungs and then will administer 3 sprays per nostril while inhaling strongly so that the drug is transported through the nose and into the lungs. The drug is to be administered 3 times per day (morning, mid-day, and evening). The product comes with instructions for administration (3 sprays per nostril).

11. Concomitant Therapy

The investigator is to record the use of all concomitant medications, both prescribed and over the counter (OTC) (including but not limited to natural food supplements), in the CRF. Subjects may continue to use their normal therapy as long as they list it as a current medication, and it is not prohibited by the exclusion criteria. Allowable concomitant therapy includes antiviral, antibiotic, antimicrobial, corticosteroids, antihistamines, or anti-inflammatory medications. The clinician may prescribe "rescue medication" should it be required by any of the patients. Patients may continue taking nutritional supplements as long as they do not contain pyruvate.

Subjects may not use any of the following during the trial or for 1 week before enrollment in the trial: all intranasal medications or lavages.

12. The Planned Maximum Dosage, and the Duration of Individual Patient Exposure to the Drug

This is a constant dose study. The amount of delivered sodium pyruvate was determined in prior clinical trials to be 3 sprays of 0.2% (2.2 mg/mL) sodium pyruvate in 0.9% sodium chloride solution per nostril, 3 times per day. The dose was determined by evaluating the data from both animal and human studies (cited above). Patients will forcibly expel air from their lungs and then will administer 3 sprays per nostril while inhaling strongly so that the drug is transported through the nose and into the lungs. The drug is to be administered 3 times per day (morning, mid-day, and evening). The product comes with instructions for administration (3 sprays per nostril).

13. A Description of the Observations and Measurements to be Made to Fulfill the Objectives of the Study

Observations for safety will include a pregnancy test for women of child-bearing age, blood tests for organ function, and vital signs. Adverse events will be monitored.

Observations for efficacy will include evaluation of lung function, as determined by FEV₁, FVC, nasal inflammation and erythema, and number of daily coughs.

13.1. Testing Schedule

Test	Screening	Day 1; 0,1,2,3 Hours	Day 8	Day 14	Day 22
Clinic Visit	+	+	+	+	+
Informed Consent	+				
Medical History	+				
Physical Exam/	+	+		+	+
Product Eval Q	+			+	+
CDRQ	+		+	+	+
Administer Drug		+	+	+	+
Blood Sample	+			+	+
Vital Signs	+	+	+	+	+
Pregnancy Test for Females	+				
Concurrent Medications Taken	+	+	+	+	+
SaO ₂	+	+	+	+	+
Nasal Inflammation	+	+	+	+	+
FEV ₁	+	+	+	+	+
FVC	+	+	+	+	+
Coughing Data Logbook*	+	+	+	+	+
Adverse Events			+	+	+
Phase Product Evaluation.	+	+	+	+	+

*The coughing data logbook will be filled out by the patient every day, starting at the pre-study visit through day 14.

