24.2. Examples of Adverse Events

- Inter-current illnesses
- Injuries
- New symptomatology (this does not include symptoms expected as a result of the subject's condition unless it is beyond what is normally expected)
- Significant laboratory abnormalities
- New abnormal physical exam findings
- Significant exacerbation of pre-existing conditions
- Death
- A life-threatening event
- In-patient hospitalization (not required as part of the treatment) or prolongation of existing hospitalization
- Disability or permanent damage
- A congenital anomaly/birth defect
- Cancer
- Drug overdose

24.3. Recording and Documentation of Adverse Events

Any adverse event (i.e., a new adverse event or an exacerbation of a pre-existing condition) with an onset date after study enrollment should be recorded as an adverse event on the CRF. All adverse events must be recorded on the appropriate CRF regardless of the severity or relationship to study medication. An adverse event or laboratory abnormality with an onset date before study enrollment is considered to be pre-existing in nature. These pre-existing events will be noted in the CRFs.

All SAEs occurring during this study, whether observed by the physician, nurse, or reported by the patient, will be recorded on the Florida Advanced Medical Research Adverse Events form.

24.3.1 Investigator Report of a "Serious Adverse Event" to Cellular Sciences.

Cellular Sciences (Sponsor) must be notified regarding the occurrence of any SAE that occurs after enrollment in the study protocol, regardless of the causal assessment to study medication. The procedures for reporting SAEs are as follows:

- Complete the "Serious Adverse Event Report."
- Email the SAE Report to Cellular Sciences (see below) within 24 hours of the investigator's knowledge of the event.
- These preliminary reports must be followed by detailed descriptions that include copies of hospital case reports, autopsy reports, and other documents when requested and applicable. Cellular Sciences may request additional information from the Investigator to ensure the timely completion of accurate safety reports.

The contact information for reporting SAEs is as follows:

[name].	[name].
Director	Director
Cellular Sciences	Cellular Sciences
[name]	[name]
[name]	[name]
[contact]	[contact]

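### SaO2, FEV1 and FVC are measured after dosing with a spray meant to reach the lungs, but they are not safety observations, no fall is defined as aberrant, and no safety summary of them is planned

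*Combined protocol and SAP*

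**What the plan says.** All references are to the combined protocol and SAP.

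- **Delivery.** Section 5.2 has the patient spray and "then forcefully inhaling the drug so that the drug is inhaled into the lungs". Section 12 repeats the intent: "inhaling strongly so that the drug is transported through the nose and into the lungs".
- **Safety observations.** Section 13: "Observations for safety will include a pregnancy test for women of child-bearing age, blood tests for organ function, and vital signs". The next sentence is "Adverse events will be monitored".
- **Efficacy observations.** Section 13: "Observations for efficacy will include evaluation of lung function, as determined by" FEV1 and FVC, together with nasal findings and daily coughs. SaO2 is in neither list.
- **Safety testing.** Section 13.2 names a physical exam, vital signs (weight, blood pressure, pulse, temperature), blood analysis and a urine test. FEV1 and FVC appear under a sub-item for efficacy tests. SaO2 does not appear.
- **Schedule.** Section 13.1 marks SaO2, FEV1 and FVC at screening, in the column "Day 1; 0,1,2,3 Hours", and on Days 8, 14 and 22.
- **Handling of abnormal results.** Section 5.2 describes the 1-, 2- and 3-hour assessments as covering both efficacy and safety. Section 15 treats every aberrant value during the study as an adverse event and leaves continuation to the principal investigator. It gives no definition of aberrant.
- **Analysis.** Section 20.2 plans a repeated-measures ANCOVA with within-treatment and between-treatment comparisons, and applies it to FEV1 and FVC as secondary outcomes. It does not name SaO2 and describes no safety analysis.

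**The concern.** The product is deliberately drawn into the lungs of patients whose lung function is already reduced. The measures most likely to show a harmful respiratory effect are collected, yet the plan uses two of them only to look for benefit and gives the third no stated use. Section 2.2 sets an improvement in FEV1 and FVC of 12% or more as an objective, and there is no corresponding count of patients who get worse.

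At stake is whether the safety report can answer an obvious question: how many patients in each arm lost lung function or desaturated after dosing? As written, the answer depends on which falls an investigator chose to call aberrant, and the planned summaries of FEV1 and FVC are group comparisons.

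**Working it through.** The plan gives no figure to reproduce. The main check sets the passages side by side; a short illustration follows.

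**1. Are the measures designated for safety?** Sections 13 and 13.2 agree with each other: FEV1 and FVC are efficacy measures, and SaO2 is in neither class. The wording of Section 13 is inclusive, so it does not forbid a safety use, but it does not provide for one.

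**2. Are post-dose data available?** Yes. If the Day 1 mark applies to all four listed hours, each patient has 3 post-dose readings on Day 1 (1, 2 and 3 hours) and 3 later ones (Days 8, 14 and 22), so 3 + 3 = 6 readings per measure. At 25 patients per arm (Section 6.1) that is 6 × 25 = 150 readings per measure per arm if complete.

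**3. Does the aberrant-value clause pick up a fall?** It can, but not reproducibly.
- No limit or change criterion is given. Section 6.1 admits patients with FEV1 and FVC down to 50% of predicted, and Section 1.1.1 attributes reduced FEV1, FVC and SaO2 to the disease. A value outside the usual range is therefore expected, and only a change criterion would separate a new fall from the patient's normal state.
- Section 15 refers to tests done 3 times. That count fits the on-treatment visits on Days 8, 14 and 22, or the three blood-sample marks in Section 13.1 (screening, Days 14 and 22). Neither reading takes in the Day 1 post-dose readings, although the sentence on aberrant values is not itself tied to the count.
- The adverse-event row in Section 13.1 appears blank for Day 1, although Section 5.2 plans safety evaluations that day. This may be an artefact of how the table was read.
- Section 16 describes 30 minutes of on-site monitoring after the first dose, while Section 5.2 has evaluations to 3 hours.

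**4. Would the planned analysis show individual falls?** The within-treatment and between-treatment comparisons in Section 20.2 both work on group averages. To illustrate, assume that k of 25 patients lose 15% of FEV1 and the rest gain 2%. These values are not from the documents. The arm mean is [(25 − k) × 2 + k × (−15)] / 25, and the interval is Clopper-Pearson.

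| k | Arm mean | Proportion with a fall | Exact 95% CI |
|---|---|---|---|
| 1 | (48 − 15)/25 = +1.32% | 4% | 0.1% to 20.4% |
| 2 | (46 − 30)/25 = +0.64% | 8% | 1.0% to 26.0% |
| 3 | (44 − 45)/25 = −0.04% | 12% | 2.5% to 31.2% |

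With k = 2 the mean is still positive, only 2 − 0.64 = 1.36 points below what it would be with no falls.

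**5. Would a per-patient count have anything to show?** If the true rate of such a fall is p, the chance of at least one among 25 is 1 − (1 − p)^25: 72% for p = 5%, 93% for p = 10% (1 − 0.072 = 0.928), and 99.6% for p = 20%. These rates are also assumed.

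**The case against.** A reader might infer that a fall in SaO2, FEV1 or FVC is never assessed as harm. The documents do not support that.

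- Section 13 adds adverse-event monitoring directly after the list of safety observations.
- Section 5.2 gives the 1-, 2- and 3-hour assessments a safety purpose as well as an efficacy one.
- Section 15 makes all aberrant values adverse events, without restricting this to blood tests.
- Section 14 withdraws a patient whose deterioration compromises safety, and Section 24.2 lists a significant exacerbation of a pre-existing condition as an adverse event.

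A reader might also infer that Section 24.2 removes such falls from adverse-event reporting, because its entry on new symptoms says "this does not include symptoms expected as a result of" the patient's condition. But that entry makes an exception for anything beyond what is normally expected, and it concerns symptoms, not measured values.

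Nor is it right that FEV1 and FVC are compared only between arms: Section 20.2 also plans within-treatment comparisons.

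Two further objections are fair. The illustration rests on assumed values and shows only that means can conceal outliers. And Section 20.2 describes no safety tabulation of any kind, including for blood tests and vital signs, so the gap is wider than these three measures. Blood tests and vital signs are at least named as safety observations, however, and these three bear most directly on the organ the spray is meant to reach.

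What remains after these objections is the missing designation, the undefined criterion and the missing summary. None of the clauses above supplies any of them.

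**Conclusion.** The point holds in a limited form. SaO2, FEV1 and FVC are measured repeatedly after dosing but are not designated as safety observations. No fall in them is defined as aberrant, Section 20.2 plans no safety summary of them, and SaO2 has no stated analysis. A fall can be recorded as an adverse event, but that depends on investigator judgement, and the planned group means could miss it: under the assumed values, two or three affected patients of 25 leave the arm mean between +0.64% and about zero.

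This rests on the text of Sections 5.2, 13 to 13.2, 15 and 20.2, and on reading the Day 1 schedule mark as covering all four hours. The blank Day 1 adverse-event cell is not relied on. The efficacy analysis is not affected.

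**What to change.** - **Sections 13 and 13.2:** add SaO2, FEV1 and FVC to the safety observations, keeping the efficacy role of FEV1 and FVC.
- **Section 20.2:** add one descriptive safety table by arm, giving (a) the lowest post-dose value and the change from the Day 1 pre-dose value at 1, 2 and 3 hours and on Days 8, 14 and 22; (b) the distribution of SaO2 change; and (c) the number of patients whose FEV1 or FVC falls beyond a cut-off that the sponsor fixes before unblinding. A 12% cut-off would mirror the improvement threshold in Section 2.2. It would serve for tabulation only, not as a rule for managing patients, and the sponsor may choose another.
- **Reconcile:** the count of 3 test occasions in Section 15 with the schedule; the apparently blank Day 1 adverse-event cell in Section 13.1 with the Day 1 safety evaluations in Section 5.2; and the 30-minute monitoring in Section 16 with the evaluations to 3 hours in Section 5.2.

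The cost is protocol wording and one extra table from data already collected. Counts at 25 per arm will be small and their intervals wide, so the table should be labelled descriptive. The efficacy analysis stays as it is.

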13.2. Safety Testing

- Physical Exam
- Vital Signs
- Weight
- Blood pressure
- Pulse
- Temperature
- Blood analysis
- Complete blood count (CBC)
- Clinical tests, including:
 - Urea nitrogen: serum creatinine: total protein: serum albumin: total globulin: albumin/globulin ratio: total bilirubin: alkaline phosphatase: aspartate aminotransferase (AST or SGOT): alanine aminotransferase (ALT or SGPT): LDH: GGT: serum sodium: potassium: chloride serum: carbon dioxide: total cholesterol:hdl ratio:
- Urine test for women of child-bearing age

- Efficacy tests
 - o Nasal examinations by a rhinoscope fitted with a camera
 - \circ FEV₁, FVC

14. Withdrawal Criteria

The patients can withdraw from the study at any time, and for any reason. All data collected from these patients will be analyzed. Reasons for withdrawal will be recorded to insure that it was not due to an adverse event.

The subject has the right to withdraw from the study at any time.

The subject will be withdrawn from the study if:

- There is deterioration in the subject's signs and symptoms and/or the subject develops a disease or condition that, in the opinion of the investigator, would compromise the subject's safety by continuing in the study.
- In the investigator's judgment, it is in the best interest of the subject.
- There is a violation of the protocol inclusion and/or exclusion criteria, as deemed relevant by the investigator and discussed with the medical monitor.
- The subject begins to take any medication(s) that is(are) excluded by the protocol.
- Any of the conditions for stopping rules are met.

If a subject withdraws prematurely from the study due to the above criteria or any other reason, study staff should make every effort (at withdrawal) to complete the full set of evaluations listed for the early termination/end-of-study visit. The reason for subject withdrawal must be documented in the case report form (CRF).

If a subject withdraws from the study due to an adverse event (AE) (eg, clinical signs, symptoms, or clinically significant laboratory abnormality), the subject will be asked to return to the clinic, at a minimum, for the evaluations scheduled for the posttreatment follow-up period. If the AE has still not resolved, additional follow-up will be performed, as appropriate, and documented in the subject's medical records. As a minimum requirement, AEs should be followed for 30 days after the subject's last dose of study medication.

In the case of a subject lost to follow-up, attempts to contact the subject must be made and documented in the subject's medical records.

Withdrawn subjects will not be replaced.

15. A Description of Clinical Procedures, Laboratory Tests, or Other Measures to be Taken to Monitor the Effects of the Drug in Human Subjects and to Minimize Risk

Tests and analyses will be conducted 3 times during the study. If any aberrant values occur, the principal investigator will determine if that patient should continue in the study or be removed. All aberrant values that occur during the study will be considered adverse events. A summary of possible risks will be provided to the patients. Previous risks of using the product are minimal, which included irritation to the nose cavity reported by 1 patient out of 1,869.

16. Safety Precautions Included in this Study

The 0.2% nasal sodium pyruvate inhalation has been administered to both healthy humans and humans with lung diseases, without the occurrence of any SAE.

- First administration of nasal spray on the premises of a hospital/clinic.
- The initial nasal spray will be administered under the supervision of medical staff.
- If a subject develops any adverse event during the follow-up period after study drug administration, the subject will be treated to a satisfactory resolution before being discharged from the clinic.
- Subjects will remain at the test site for monitoring for 30 minutes after the initial inhalation of the nasal spray.
- Follow up telephone communications, as needed.

17. Product Evaluation Questionnaire

This self-administered questionnaire measures the patients' impressions of how the drug affected their nasal cavity, their coughing, and their breathing. It is designed to evaluate changes in a subject's quality of life over time. It will be administered during all clinic visits.

18. Daily Data Logbook

Subjects will use this diary card to record the number of their coughs per day, any self-perceived adverse events, and any medication changes during the study.

19. Urinalysis

Samples will be taken and analyzed to determine if any child-bearing females are pregnant.

20. Study Management

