20.2. Data Collection, Management, and Statistical Analysis

The data management staff at the research clinic will collect and manage the data. Data will be obtained, maintained, and transmitted securely in accordance with HIPAA guidelines. Monitoring and auditing of the data will be conducted by a staff member of Cellular Sciences.

Statistical analysis will be performed on deidentified data. The basic statistical analysis will be repeated measurements of Analysis of Variance using baseline measurements as a covariant (ANCOVA). Age, sex, time since initial diagnosis with IPF, concurrent medications and smoking status are considered potential covariates. Number of coughing episodes reported for a 24-hour pre-study period, and other pre-study data information, will be compared to the data collected during the trial. The differences between baseline data and the data collected during the trial will be compared and analyzed (Within treatment). Additionally, the data of the patients on the experimental therapy will be compared to the data generated by the patients on placebo (Between treatments). P values of <0.5 will be considered significant. FEV1 and FVC will similarly be analyzed as secondary outcome measurements. Relative changes will be analyzed by JMP, Matillion, XLSTAT or R software by [name] or [name], who will be responsible for the statistical analysis.

Partial patient data will be included in the statistical analysis if patients withdraw from the study, but data from non-compliant patients will be excluded. Our previous research (REF) indicates that a sample size of 20 is sufficient to detect a statistically significant difference (p<0.05) between treatment groups. We have chosen to enroll 25 patients in each treatment group to ensure we achieve the necessary sample size, taking into account that some patients may not complete the study, and some data will be incomplete or excluded from the study.

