20.3. Data from Patients who Withdraw from the Study

If a subject withdraws from a study, the data collected on the subject to the point of withdrawal will remain part of the study database and will not be removed.

The investigator may ask a subject who is withdrawing whether the subject wishes to provide continued follow-up and further data collection subsequent to their withdrawal from the interventional portion of the study. Under this circumstance, the discussion with the subject would distinguish between study-related interventions and continued follow-up of associated clinical outcome information, such as medical course or laboratory results obtained through non-invasive chart review and address the maintenance of privacy and confidentiality of the subject's information.

If a subject withdraws from the interventional portion of the study but agrees to continued follow-up of associated clinical outcome information as described in the previous paragraph, the investigator must obtain the subject's informed consent for this limited participation in the study (assuming such a situation was not described in the original informed consent form). In accordance with FDA regulations, Institutional Review Board (IRB) approval of informed consent documents would be required (21 CFR 50.25, 56.109(b), 312.60, 312.66, 812.100).

If a subject withdraws from the interventional portion of a study and does not consent to continued follow-up of associated clinical outcome information, the investigator must not access for purposes related to the study the subject's medical record or other confidential records requiring the subject's consent. However, an investigator may review study data related to the subject, collected prior to the subject's withdrawal from the study, and may consult public records, such as those establishing survival status.

21. Product Packaging

The product packaging will comply with FDA regulations. The nasal spray will be contained in a sterile plastic vial that can be squeezed to administer the correct dosage. The vials necessary for each study period (i.e. 14 days) will be placed in a paperboard box in a plastic bag with the patient's number.

22. Product Storage Requirements

At Research Center

The products will be stored at room temperature, but not above 85°F.

In Home

The products will be stored at room temperature, but not above 85°F.

23. Record Retention

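### Sections 14 and 15 take patients out of the study rather than just off the spray, and no scheduled cough log or spirometry follows them to Day 22

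*Combined protocol and SAP*

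**What the plan says.** Section 14 opens its mandatory list with "The subject will be withdrawn from the study if". The triggers include deterioration or a new condition "that, in the opinion of the investigator, would compromise the subject's safety by continuing in the study", and also this one: "The subject begins to take any medication(s) that is(are) excluded by the protocol". The medication trigger is narrow. Section 11 bars intranasal products and pyruvate-containing supplements but allows corticosteroids, anti-inflammatories and rescue medication.

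Section 15 adds a discretionary route: for aberrant values, "the principal investigator will determine if that patient should continue in the study or be removed".

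The plan provides the following after exit:

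- Section 14: staff try to complete the early-termination evaluations at the time of withdrawal.
- Section 14, adverse-event exits only: a return visit "for the evaluations scheduled for the posttreatment follow-up period", with adverse events followed for at least 30 days after the last dose. The Section 13.1 schedule ends at Day 22 and shows no such period.
- Section 20.3: the investigator may ask about continued follow-up. The examples given are "medical course or laboratory results obtained through non-invasive chart review".

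Data up to withdrawal are kept and analysed (Sections 14, 20.2 and 20.3). Section 20.2 names a repeated-measures ANCOVA without saying how incomplete records are handled, and adds that "data from non-compliant patients will be excluded". Section 14 also states that withdrawn subjects are not replaced.

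**The concern.** The primary objective is cough and the secondary objective is FEV1 and FVC. A patient removed for deterioration may be leaving because of the very outcome under study. Such exits could be more frequent on placebo if N115 works, or more frequent on N115 if it irritates the nose.

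Once the patient has left, nothing keeps the daily log or the remaining Day 8, 14 and 22 spirometry going. The analysis must then rely on an assumption about the missing course. A likelihood-based repeated-measures model is unbiased if exit depends only on values already recorded. It is not unbiased if exit follows worsening that never reached the log or a visit. The plan neither states that assumption nor provides a sensitivity analysis, and outcomes not collected cannot be recovered later.

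**Working it through.** **Inputs from the protocol.** The target is a 25% reduction (Section 2.1). There are 25 patients per arm, enrolled to secure 20 (Sections 6.1 and 20.2), so one patient is 1/25 = 4% of an arm. No withdrawal rate, SD or outcome difference for withdrawn patients is given.

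**The plan's own figure.** The 20 per group cannot be reproduced, because no effect size, SD or power is stated. The step to 25 can: 20 / (1 − 0.20) = 25. The plan therefore tolerates losing up to 5 of 25 per arm, from all causes including excluded data.

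**Shift on the log scale.** Let w be the share of an arm that exits. Let d be how far the unrecorded later cough of those patients exceeds, in logs, what the analysis assumes for them (taken equal in both arms). Each arm's mean is then understated by w × d, so

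estimated log ratio = true log ratio + (w_placebo − w_N115) × d.

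With true log ratio ln 0.75 = −0.2877 and assumed exits and d:

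| Exits, placebo / N115 | d | Shift | Estimated reduction |
|---|---|---|---|
| 1 / 0 | ln 1.25 = 0.2231 | 0.04 × 0.2231 = +0.009 | 24.3% |
| 4 / 1 | ln 1.5 = 0.4055 | 0.12 × 0.4055 = +0.049 | 21.3% |
| 1 / 4 | ln 1.5 = 0.4055 | −0.12 × 0.4055 = −0.049 | 28.6% |
| equal, or d = 0 | any | 0 | 25.0% |

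With no true effect, the 1 / 4 row gives a spurious reduction of 1 − exp(−0.049), about 4.7%.

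**A second calculation, as an outer range.** Suppose only completers are compared, and withdrawn patients would be D percentage points worse at Day 22 than completers in their own arm. The bias is (w_placebo − w_N115) × D. With all 5 losses in one arm (w = 0.20), it is ±2.5 points for D = 12.5, ±5 for D = 25 and ±10 for D = 50. This is harsher than the plan, which keeps partial data.

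**When the problem disappears.** A simulation with 400,000 patients per arm (assumed SD 0.5, correlation 0.6), in which exit depends only on recorded weeks and the analysis is likelihood-based, returns 25.1% at overall withdrawal of 5%, 10% and 20%. The bias comes from the unrecorded part.

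**The case against.** The strongest reply is that little worsening would go unrecorded. Section 5.2 has cough logged daily and patients phoned every two days, and Section 14 asks for a full evaluation at exit. This makes d smaller, but those records stop at exit, and the plan does not commit to an analysis that would use them properly.

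The numbers are assumed and modest. Even a 4-to-1 imbalance with a 50% excess moves 25% by less than four points, and the allowance of 5 per arm is not specific to Section 14 exits. That stands, and it limits the weight of the point.

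The scenario with more N115 exits has thin support. Section 15 reports nasal irritation in 1 of 1,869 patients, both arms share the preservative, and Section 1.1.4 ties irritation to higher concentrations. It cannot be ruled out, but it is the less likely direction.

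Section 15 removal is discretionary, and no link between laboratory values and cough is shown. Section 20.3 does separate the intervention from follow-up, its chart-review examples are only examples, and the consent form may already cover more. Even so, that follow-up is optional and does not name the log or spirometry.

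Finally, including data after stopping is partly a choice of estimand. Section 1.1.6 claims an effect of 4–6 hours, so cough after stopping is essentially off-drug cough. The dilution is real. It also means the table's 25%, taken as true for everyone, is a simplification for N115 patients who stop. Collecting the data still leaves either question answerable.

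**Conclusion.** The concern holds. As written, the triggers end participation, some can be related to outcome, and no provision after exit secures the cough log or spirometry to Day 22. On the assumed inputs of the log-scale calculation, the estimate moves from a true 25% to between 21.3% and 28.6%, with no shift when exits are balanced or the analysis predicts the missing course correctly. The sign depends on which arm loses more patients, and the plan cannot determine it.

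Confidence is medium, because exit counts, d and the equality of d across arms are all assumptions and few exits may occur in 21 days. This should be changed because the remedy is cheap and the loss irreversible, but it does not by itself invalidate the trial.

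**What to change.** Reword Section 14 along these lines: *Study drug is stopped if any of the following occurs. Unless the subject withdraws consent, the daily log, the telephone contacts and the remaining Day 8, 14 and 22 assessments continue as scheduled to Day 22.* Any assessment that would itself be unsafe is omitted.

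Then:

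- Use the same wording for removal under Section 15.
- Name Day 22 explicitly, because the Section 13.1 footnote has the logbook "starting at the pre-study visit through day 14" while Section 5.2 requires 21 days.
- Align Section 20.3, and the consent form if it does not already cover this.
- Record the date and reason for stopping, and include data after stopping in the main analysis.
- State that stopping the spray under Section 14 or 15 is not non-compliance under Section 20.2; otherwise the retained data could still be dropped.

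The cost is protocol wording and possibly consent wording, since visits and calls already run to Day 22. The downside is some dilution of a pure on-drug effect, because part of the later data reflects other therapy or none.
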